2.4.4.3 Analyses of other efficacy endpoints

The analysis of other endpoints (see [Section 2.1.3](#)) will be descriptive with no formal testing. Summary statistics at scheduled visits based on observed value will be provided by each treatment group. Graphical presentations will also be used to illustrate trends over time as appropriate.

The number (%) of patients who used rescue therapy and a KM curve for the time to first rescue therapy will be provided by treatment group. A list of patients who used rescue therapy will also be provided (see [Section 2.5.4](#)).

Urine ACR will be log-transformed at patient level. Summary statistics of urine ACR in log scale will then be calculated for each treatment group at each visit and back-transformed to provide the geometric mean and its associated percent change of urine ACR from baseline.

Shift tables will be provided for urine ACR at Week 26 using the pre-defined categories. That is, the number (%) of patients with progression from one category at baseline to another category at Week 26 will be provided by treatment group. The pre-defined categories are, for urine ACR, < 30 mg/g creatinine [Normal], ≥ 30 to < 300 mg/g creatinine [Microalbuminuria], and ≥ 300 mg/g creatinine [Macroalbuminuria].

The analysis of the 2-hour PPG endpoint will be based on a Time 0 adjusted value (ie, the 2-hour PPG value minus the Time 0 value, FPG sample) at both the Baseline and Week 26 time points. These Time 0 adjusted values will be used to derive the Week 26 minus Baseline scores, which will serve as the measure of interest for comparative purposes.

Statistical Analysis Plan

Version: 3

Lexicon Pharmaceuticals Protocol No. EFC14833

Date of Issue: 21-Nov-2019

Covance Study ID: 000000150524

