1.2.2 Secondary objectives

- To compare sotagliflozin 400 mg versus placebo for:
 - Change from Baseline in 2-hour postprandial glucose (PPG) following a mixed meal (MM) at Week 26
 - Change from Baseline in fasting plasma glucose (FPG) at Week 26
 - Change from Baseline in body weight at Week 26,
 - Change from Baseline in SBP at Week 12 for patients with baseline SBP \geq 130 mmHg,
 - Change from Baseline in SBP at Week 12 for all patients,
 - Proportion of patients with HbA1c <6.5%, <7.0% at Week 26
- To compare sotagliflozin 200 mg versus placebo for:
 - Change from Baseline in HbA1c at Week 26
 - Change from Baseline in 2-hour PPG following a MM at Week 26
 - Change from Baseline in body weight at Week 26,
 - Change from Baseline in SBP at Week 12 for all patients.
- To evaluate the safety of sotagliflozin 400 mg and 200 mg doses versus placebo

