2.1.3.2 Secondary efficacy endpoint(s)

The secondary efficacy endpoints are:

- Comparison of sotagliflozin 400 mg versus placebo for,
 - Change from Baseline to Week 26 in 2-hour PPG following a MM
 - Change from Baseline to Week 26 in FPG
 - Change from Baseline to Week 26 in body weight
 - Change from Baseline to Week 12 in SBP for patients with baseline SBP \geq 130 mmHg
 - Change from Baseline to Week 12 in SBP for all patients
 - Proportion of patients with HbA1c <6.5%, <7.0% at Week 26

Statistical Analysis Plan

Version: 3

Lexicon Pharmaceuticals Protocol No. EFC14833

Date of Issue: 21-Nov-2019

Covance Study ID: 000000150524

- Comparison of sotagliflozin 200 mg versus placebo for,
 - Change from Baseline to Week 26 in HbA1c
 - Change from Baseline to Week 26 in 2-hour PPG following a MM
 - Change from Baseline to Week 26 in body weight
 - Change from Baseline to Week 12 in SBP for all patients.

2.1.3.3 *Other efficacy endpoint(s)*

Comparison of sotagliflozin 400 mg and 200 mg doses versus placebo for,

- Change from Baseline to Week 12 in SBP for patients with baseline SBP <130 mmHg
- Changes from Baseline to Week 12 in diastolic blood pressure (DBP)
- Proportion of patients achieving SBP <130 mmHg for those with Baseline SBP \geq 130 mmHg
- Proportion of patients achieving DBP <80 mmHg for those with Baseline DBP \geq 80 mmHg
- Change from Baseline in:
 - Urine ACR, UGE, and urine GCR
 - Serum creatinine
 - eGFR
- Proportion of patients with reduction in body weight by \geq 2%, \geq 5%, and \geq 10% from Baseline
- Change from Baseline to Week 26 in SBP for all patients and for patients with Baseline SBP \geq 130 mmHg
- Proportion of patients requiring rescue for hyperglycemia

Comparison of sotagliflozin 200 mg versus placebo for,

- Change from baseline in FPG at Week 26
- Change from baseline in SBP at Week 12 for patients with Baseline SBP \geq 130 mmHg
- Proportion of patients with HbA1c <6.5%, <7.0% at Week 26

2.1.4 **Safety endpoints**

The safety analysis will be based on the reported adverse events, hypoglycemia, and other safety information, such as clinical laboratory data, vital signs, electrocardiogram (ECG), and physical examination, etc.

Statistical Analysis Plan

Version: 3

Lexicon Pharmaceuticals Protocol No. EFC14833

Date of Issue: 21-Nov-2019

Covance Study ID: 000000150524

Observation period

The observation period will be divided into 4 epochs:

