2.4.4.2 Analyses of secondary efficacy endpoints

For continuous secondary efficacy parameters (see [Section 2.1.3](#)) with missing data at baseline, missing data will be imputed using MI under the missing at random (MAR) assumption. Missing data at baseline will be imputed using regression method that includes randomization stratum of HbA1c (\leq 8.0%, $>$ 8.0%), randomization stratum of SBP (<130 mmHg, \geq 130 mmHg), and baseline value in the imputation model.

Each continuous secondary efficacy endpoint ([Section 2.1.3](#)) will be analyzed using a similar ANCOVA model including the measurements at baseline and endpoint (observed or imputed). The missing data at endpoint will be imputed by the retrieved dropouts if there are at least 5 patients in each study treatment group who discontinued but have the endpoint. Otherwise, the

Statistical Analysis Plan

Version: 3

Lexicon Pharmaceuticals Protocol No. EFC14833

Date of Issue: 21-Nov-2019

Covance Study ID: 000000150524

washout imputation method will be used according to the criterion described in Section 2.4.1. After the imputation, each of the complete datasets will be analyzed by an ANCOVA model.

- To compare sotagliflozin 400 mg versus placebo under the original protocol and Amendment 1, the ANCOVA model will include treatment groups (sotagliflozin 400 mg, placebo), randomization stratum of HbA1c ($\leq 8.0\%$, $> 8.0\%$), randomization stratum of SBP (< 130 mmHg, ≥ 130 mmHg), and country as fixed effects, and the corresponding baseline value as a covariate.
- To compare sotagliflozin 200 mg versus placebo under Amendment 1, the ANCOVA model will include treatment groups (sotagliflozin 200 mg, placebo), randomization stratum of HbA1c ($\leq 8.0\%$, $> 8.0\%$), randomization stratum of SBP (< 130 mmHg, ≥ 130 mmHg), and country as fixed effects, and the corresponding baseline value as a covariate.

For the analysis of SBP in patients with baseline SBP ≥ 130 mmHg, the randomization stratum of SBP will not be included in the ANCOVA model. Results from each complete dataset will be combined using Rubin's formula to provide the adjusted mean change from Baseline to Week 26 (or Week 12 for SBP) for each treatment group, as well as the between-group difference (comparing each sotagliflozin dose group vs its corresponding placebo group) and the 95% CI for the difference.

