2.4.4.4 Multiplicity issues

To control the family-wise type I error, a fixed-sequence procedure will be applied.

Once the primary variable (change from Baseline to Week 26 in HbA1c) is statistically significant at $\alpha = 0.05$ (2-sided), the following secondary efficacy variables will be tested in the following prioritized order. The testing will stop as soon as an endpoint is found not to be statistically significant at $\alpha=0.05$ (2-sided).

- Comparing sotagliflozin 400 mg versus placebo,
 - Change from Baseline to Week 26 in 2-hour PPG following an MM
 - Change from Baseline to Week 26 in FPG
 - Change from Baseline to Week 26 in body weight
 - Change from Baseline to Week 12 in SBP for patients with baseline SBP ≥ 130 mmHg
 - Change from Baseline to Week 12 in SBP for all patients
 - Proportion of patients with HbA1c $< 7.0\%$ at Week 26
- Comparing sotagliflozin 200 mg versus placebo,
 - Change from Baseline to Week 26 in HbA1c
 - Change from Baseline to Week 26 in 2-hour PPG following an MM
 - Change from Baseline to Week 26 in body weight
 - Change from Baseline to Week 12 in SBP for all patients.

No multiplicity adjustment will be made on efficacy variables other than those mentioned above.

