Appendix D Summary of statistical analyses

EFFICACY ANALYSIS

Endpoint	Analysis population	Primary analysis	Supportive analysis	Subgroup analysis	Other analyses
Primary endpoint					
HbA _{1c} : Change from baseline at Week 26, (sotagliflozin 400 mg vs placebo)	ITT	ANCOVA (with missing values imputed by the retrieved dropouts & washout imputation method or by control-based copy reference MI method under MNAR framework): treatment, randomization stratum (HbA _{1c} / SBP at screening), and country as fixed effects, and baseline HbA _{1c} value as a covariate, under the original protocol and Amendment 1	Tipping point analysis; ANCOVA (with missing values imputed by the retrieved dropouts & washout imputation method or by control-based copy reference MI method under MNAR framework) under original protocol and Amendment 1	Subgroups: race, ethnicity, age, gender, baseline BMI, baseline HbA _{1c} , baseline SBP, baseline eGFR and country.	Summary statistics for observed values and changes from baseline by visit. Graphical presentations for mean changes from baseline (\pm SE) and mean values (\pm SE) by visit. By-visit summary and graph excluding measurements after rescue therapy.
Secondary endpoints					
HbA _{1c} , 2-hour PPG, FPG, body weight: Change from Baseline to Week 26; SBP (for patients with baseline SBP \geq 130 mmHg, all patients): Change from Baseline to Week 12	ITT	ANCOVA (with missing values imputed by the retrieved dropouts & washout imputation method or by control-based copy reference MI Method under MNAR framework): treatment, randomization stratum (HbA _{1c} / SBP at screening), and country as fixed effects, and baseline HbA _{1c} value as a covariate, comparing sotagliflozin 400 mg vs placebo under the original protocol and Amendment 1, and comparing sotagliflozin 200 mg vs placebo	ANCOVA (with missing values imputed by the retrieved dropouts & washout imputation method or by control-based copy reference MI method under MNAR framework) comparing sotagliflozin 200 mg (for selected other endpoints) vs placebo under Amendment 1; Tipping point analysis on HbA _{1c} .	Subgroups on HbA _{1c} : race, ethnicity, age, gender, baseline BMI, baseline HbA _{1c} , baseline SBP, baseline eGFR and country.	Summary statistics for observed values and changes from baseline by visit. Graphical presentations for mean changes from baseline (\pm SE) and mean values (\pm SE) by visit.

Statistical Analysis Plan

Version: 3

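### The first gated secondary test, 2-hour PPG, has two definitions: the SAP analyses a fasting-adjusted excursion, while the protocol and the rest of the SAP name the change in 2-hour PPG itself

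*SAP*

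**What the plan says.** Most of the text names one variable. SAP 1.2.2 has "Change from Baseline in 2-hour PPG following a MM at Week 26", SAP 2.1.3.2 has "Change from Baseline to Week 26 in 2-hour PPG following a MM", and the fixed sequence in SAP 2.4.4.4 has "Change from Baseline to Week 26 in 2-hour PPG following an MM". SAP Appendix D groups it with the other continuous secondaries: "2-hour PPG, FPG, body weight: Change from Baseline to Week 26". The protocol uses the same endpoint in its synopsis and in sections 5.2, 9.1.2, 9.1.4.2 and 11.4.2.4. None of these places subtracts a fasting value.

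SAP 2.4.4.3 says something else: "The analysis of the 2-hour PPG endpoint will be based on a Time 0 adjusted value". The fasting (Time 0) glucose is taken off the 2-hour value at Baseline and at Week 26, and the difference between the two adjusted values is the quantity "which will serve as the measure of interest for comparative purposes". That section covers the other efficacy endpoints, whose analysis "will be descriptive with no formal testing".

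SAP 2.4.4.2, which governs the continuous secondary endpoints, contains no Time 0 step and does not refer to 2.4.4.3. Its ANCOVA has strata "and country as fixed effects, and the corresponding baseline value as a covariate". Appendix D instead lists baseline HbA1c as the covariate for all continuous secondaries.

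**The concern.** The 2-hour PPG is not among the other endpoints in either document. Its only listed role is as a tested secondary endpoint for each dose, so a rule about its comparative analysis can only bear on those confirmatory tests. The rule is nevertheless placed where no testing is planned, and the sections that do set up the tests are silent on it.

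At stake is the meaning of the first secondary test and the passage through it. The excursion measures the glucose rise after the meal; the 2-hour value also includes the fasting level. A drug that lowers fasting glucose will move the two differently. A significant excursion would not by itself establish the stated objective on 2-hour PPG, and a non-significant one at 400 mg would stop the sequence, including every 200 mg test. While both definitions stand in the text, either choice can be supported or challenged from the sponsor's own documents, and the choice could be made with results in hand.

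**Working it through.** **1. The plan's own figures.** No power is stated for PPG. The nearest figures are for HbA1c (SAP 1.3: SD 1.2, two-sided 0.05, 100 per arm). A two-sample noncentral t calculation gives 94.0% for a difference of 0.6 (stated 94%) and 83.4% for 0.5 (stated 84%). Both reproduce. Neither depends on the PPG definition.

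**2. How the two variables differ.** Let P be the change in 2-hour PPG and F the change in FPG. SAP 2.4.4.3 analyses E = P − F. Between groups:

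- effect on E = effect on P − effect on F
- SD(E)² = SD(P)² + SD(F)² − 2 × correlation × SD(P) × SD(F)

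The target therefore changes by exactly the FPG effect, and FPG is the next test in the 400 mg sequence.

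**3. What lies behind the gate (SAP 2.4.4.4).**

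- After 400 mg PPG: FPG, body weight, SBP (baseline ≥130 mmHg), SBP (all) and HbA1c <7% make 5; the four 200 mg tests bring the total to 5 + 4 = 9.
- After 200 mg PPG: body weight and SBP (all), so 2.

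**4. Sample sizes (SAP 1.3 and 2.3).** 400 mg and pooled placebo: 76/2 + 300/3 = 138 per arm. 200 mg and its placebo: 300/3 = 100 per arm.

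**5. Illustrative power.** The documents give no PPG or FPG effects, SDs or correlation, so everything in this step is assumed. Let e be the PPG effect in SD units, f the share of it carried by FPG, and r = SD(P)/SD(E). The standardized excursion effect is e × (1 − f) × r. For example, e = 0.5, f = 0.50 and r = 1 give 0.25, and 54.4% power at 138 per arm.

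| n per arm | e | r | PPG as measured | f = 25% | f = 50% | f = 70% |
|---|---|---|---|---|---|---|
| 138 | 0.5 | 1.00 | 98.5% | 87.4% | 54.4% | 23.7% |
| 138 | 0.5 | 1.25 | 98.5% | 97.3% | 73.5% | 34.2% |
| 138 | 0.5 | 1.40 | 98.5% | 99.1% | 82.6% | 41.2% |
| 138 | 0.7 | 1.00 | >99.9% | 99.1% | 82.6% | 41.2% |
| 100 | 0.5 | 1.00 | 94.0% | 75.1% | 42.1% | 18.4% |

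r = 1.25 means an excursion SD 20% smaller than the PPG SD; r = 1.40 means 29% smaller. The latter arises, for instance, with SDs of 60 and 40 and correlation 0.7: √(3600 + 1600 − 3360) = 42.9, and 60/42.9 = 1.40. Adjustment costs no power when f ≤ 1 − 1/r, that is 0%, 20% and 28.6% for the three values of r.

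**6. How often the two tests disagree.** Simulation of both tests on the same data (20,000 runs, 138 per arm; assumed SDs 3.5 and 2.2 mmol/L, correlation 0.7) gave different significance decisions in 0.4% of trials (PPG effect 2.0, f = 25%), 8.9% (2.0, 50%), 25.6% (1.5, 50%) and 62% (2.0, 75%). With no effect on either variable, counting a success if either version is significant gave 7.7% instead of 5%.

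**7. Covariate and missing data.** The corresponding baseline in SAP 2.4.4.2 is baseline PPG or baseline excursion depending on the variable, and Appendix D names a third quantity, HbA1c. Under SAP 2.5.3 a derived variable is missing if any component is missing: the change in PPG needs two measurements and the change in excursion needs four, so the set of patients requiring imputation can differ too.

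**The case against.** The best defence is that SAP 2.4.4.3 is the operative rule. The other places are endpoint labels, none of them uses the word unadjusted, and a specific derivation normally governs a general label. Protocol 9.1.4.2 and Appendix B also collect a fasting sample as part of each meal test. On this reading the SAP does fix one variable, and what remains is a misplaced paragraph. That reading does not remove the defect: the SAP would then test something other than the protocol's endpoint, since the protocol describes a fasting sample but no subtraction, and neither the ANCOVA section nor the testing sequence would say so.

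Other points against the concern carry weight:

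- Nothing in the plan permits testing both versions, so the 7.7% only shows what choosing after the fact could cost. If one version is fixed beforehand, the sequence controls error under either.
- Several SAP change-log rows, including four of the five for version 3, are blacked out. It cannot be said that the change was unlogged or unexplained; a rationale would still not reconcile the current text.
- Protocol 9.6 calls for both fasting and postprandial glucose and does not settle which postprandial variable to use. An excursion would overlap less with the FPG test.
- The Appendix D covariate affects all continuous secondaries; it adds to the uncertainty but is not specific to PPG.
- The power table uses a t test rather than the planned ANCOVA, and full arms although the protocol bars the meal test after a premature end-of-treatment visit.

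**Conclusion.** The concern holds. The current SAP contradicts the protocol and its own other sections on the variable for the first secondary test at 400 mg and the second test at 200 mg. This must be fixed, because a gatekeeping test needs one written definition before results are seen. The position of the gate is documented: nine tests depend on the 400 mg result and two on the 200 mg result. The power consequence cannot be determined from the documents. On the assumptions shown it runs from no loss, or a slight gain, when FPG carries little of the effect and the excursion is less variable, to a severe loss when FPG carries most of it. The primary 400 mg HbA1c test is not affected.

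**What to change.** Move the PPG paragraph from SAP 2.4.4.3 to 2.4.4.2. For both doses, define the tested variable there as the change from Baseline to Week 26 in measured 2-hour PPG, with baseline 2-hour PPG as the covariate, and state that imputation is done on that variable. Keep the Time 0-adjusted excursion as a supportive analysis outside the testing sequence. Correct the covariate in Appendix D, and make 2.1.3.2, 2.4.4.2, 2.4.4.4 and Appendix D agree before unblinding.

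Moving the excursion rule to 2.4.4.2 and declaring a departure from the protocol would also end the ambiguity, but it would replace the protocol's endpoint. Testing the protocol's endpoint needs no protocol amendment. The cost is SAP wording in four places and one supportive table, with no new data.

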2.4.4.4 Multiplicity issues

To control the family-wise type I error, a fixed-sequence procedure will be applied.

Once the primary variable (change from Baseline to Week 26 in HbA1c) is statistically significant at $\alpha = 0.05$ (2-sided), the following secondary efficacy variables will be tested in the following prioritized order. The testing will stop as soon as an endpoint is found not to be statistically significant at $\alpha=0.05$ (2-sided).

- Comparing sotagliflozin 400 mg versus placebo,
 - Change from Baseline to Week 26 in 2-hour PPG following an MM
 - Change from Baseline to Week 26 in FPG
 - Change from Baseline to Week 26 in body weight
 - Change from Baseline to Week 12 in SBP for patients with baseline SBP ≥ 130 mmHg
 - Change from Baseline to Week 12 in SBP for all patients
 - Proportion of patients with HbA1c $< 7.0\%$ at Week 26
- Comparing sotagliflozin 200 mg versus placebo,
 - Change from Baseline to Week 26 in HbA1c
 - Change from Baseline to Week 26 in 2-hour PPG following an MM
 - Change from Baseline to Week 26 in body weight
 - Change from Baseline to Week 12 in SBP for all patients.

No multiplicity adjustment will be made on efficacy variables other than those mentioned above.

2.4.5 Analyses of safety data

The summary of safety results will be presented by treatment group.

The “observation period” defined in [Section 2.1.4](#) is applicable in all safety analyses for the classification of AEs, determination of treatment-emergent Potentially Clinically Significant Abnormality (PCSA) values and the last on-treatment value for the laboratory, vital sign and ECG.

General common rules

All safety analyses will be performed on the safety population as defined in [Section 2.3.2](#), unless otherwise specified, using the following common rules:

- Safety data in patients who do not belong to the safety population (eg, exposed but not randomized) will be listed separately.
- The baseline value (with the exception of serum creatinine and eGFR) is defined as the last available value before the first dose of double-blind IMP. For serum creatinine and

Statistical Analysis Plan

Version: 3

Lexicon Pharmaceuticals Protocol No. EFC14833

Date of Issue: 21-Nov-2019

Covance Study ID: 000000150524

eGFR, the baseline value is defined as the average of all values before the first dose of double-blind IMP.

- PCSA values are defined as abnormal values considered medically important by the Sponsor according to predefined criteria/thresholds based on literature review and defined by the Sponsor for clinical laboratory tests, vital signs, and ECG [Appendix B].
- PCSA criteria will determine which patients had at least 1 PCSA during the TEAE period, taking into account all evaluations performed during the TEAE period, including nonscheduled or repeated evaluations. The number of all such patients will be the numerator for the treatment-emergent PCSA percentage.
- The treatment-emergent PCSA denominator by group for a given parameter will be based on the number of patients assessed for that given parameter during the TEAE period by treatment group in the safety population.
- For laboratory parameters cited in the protocol as efficacy endpoints (including HbA1c and plasma glucose etc.), PCSA summaries will not be provided. These parameters will be summarized in efficacy [Section 2.4.4](#). For creatinine and eGFR, PCSA summaries will be presented in safety [Section 2.4.5](#) while descriptive summaries in efficacy [Section 2.4.4](#).
- For quantitative safety parameters based on central laboratory/reading measurements, descriptive statistics will be used to summarize results and change from baseline values by visit and treatment group. Summaries will include the last on-treatment value. The last on-treatment value is commonly defined as the value collected at the same day/time of the last administration of IMP. If this value is missing, this last on-treatment value will be the closest value prior to the last dose administration.
- The analysis of the safety variables will be essentially descriptive and no systematic testing is planned. Relative risks versus placebo and their 95% CIs may be provided, if relevant.
- Selected safety analyses will be summarized by age, gender, racial subgroups, and other pertinent subgroups (see details in [Section 2.4.5.1](#) and [Section 2.4.5.2](#)).

